### **6.1.2. Safety Criteria for Adjusting or Stopping Treatment**

Hypersensitivity reactions may occur to the active substance of vandetanib. Such hypersensitivity is a contraindication for BTG-002814 administration and is covered by this protocol's exclusion criterion 3.

Allergy to contrast media that cannot be managed with standard care may also cause hypersensitivity reactions. Such hypersensitivity is a contraindication for treatment with BTG002814 and is covered by this protocol's exclusion criterion 6.

Should any previously unknown hypersensitivity become apparent at any stage during treatment, administration of BTG-002814 will stop immediately and standard care indicated for hypersensitivity reactions will be initiated and completed.

Rash and other skin reactions including photosensitivity reactions and palmar-plantar erythrodysesthesia syndrome have been observed in patients who have received vandetanib. Patients will be advised to minimise exposure to the sun by wearing protective clothing and/or sunscreen due to the potential risk of phototoxicity reactions associated with vandetanib for UV light for at least four weeks following treatment (visit 2).

### **6.1.3. Post-study Management**

Management of patients after they have completed or been withdrawn from the study should be as per the investigational site's standard procedures

### **6.1.4. Duration of Treatment and Follow up**

All patients will receive one treatment of BTG-002814 between 7 and 21 days prior to surgery. All patients will be followed up for 28-32 days following surgery.

### **6.1.5. Concomitant Medications**

Concomitant medications are defined as those taken from the date of Informed Consent to the date of the final visit (Visit 6, End of Study).

Patients previously treated with other loco-regional therapies including transarterial embolisation (with or without chemotherapy), prior external beam radiation or prior yttrium-90 microsphere therapy are excluded from this study (see exclusion criterion 2).

Medicinal products known to also prolong the QTc interval and/or induce Torsades de pointes should not be used in combination with BTG-002814, and should not be administered during the study (see exclusion criterion 3). Refer to Appendix 1.

With the exception of the above, there are no concomitant medications specifically prohibited during the study, however, there are multiple known drug interactions that are relevant for the vandetanib active drug, including:

- Strong CYP3A4 inducers (e.g., rifampicin, rifabutin, St John's Wort, carbamazepine, phenytoin, barbiturates)

- Vandetanib can increase the Cmax of metformin, therefore metformin dosage monitoring is recommended.
- Vandetanib can increase the Cmax of P-gp substrates such as digoxin, therefore digoxin dosage monitoring is recommended.
- If the patient's concomitant medication includes vitamin K antagonists (e.g., warfarin, phenindione, acenocoumarol), increased frequency of INR monitoring is recommended.

Documentation of all concomitant medication, including any sedative medication used during treatment and surgery, and any over the counter medications, should continue until the final visit and must be recorded in the patient's medical notes and CRFs.

## **6.2. Investigational Product/Labeling/Packaging/Storage/Handling**

### **6.2.1. Investigational Product**

BTG-002814 is a radiopaque embolic bead pre-loaded with vandetanib. It is light brown/golden in colour and is provided lyophilized, in glass vials.

Each vial contains 1 mL of BTG-002814 containing 100 mg vandetanib when hydrated as per protocol.

BTG-002814 will be provided free of charge to the site by BTG and must not be used outside the context of this study.

### **6.2.2. Labeling and Packaging**

BTG-002814 will be labelled and packaged by BTG International Germany GmbH.

BTG-002814 vials will be sealed in an aluminium foil pouch and placed within a carton. The vial, pouch and carton will be labelled with a single panel, local language label, in accordance with good manufacturing practice (GMP) and in compliance with local law(s) and legislation. Supplies will be labelled in accordance with Annex 13 guidelines on labelling of Investigational Medicinal Products and in line with local legislation. They will contain the following at a minimum; protocol identifier, contents, directions for use, expiry date, storage, batch number, unique medication identification number i.e., vial number.

### **6.2.3. Storage and Handling**

Prior to use, BTG-002814 must be stored in a secured access, locked area, accessible only to authorised site personnel.

BTG-002814 should be stored above 8°C and must not be refrigerated or frozen.

In the event of a product complaint, the Sponsor and UCL CTC must be informed within 24 hours, including a brief description of the incident seen. The Sponsor will then investigate and inform the site on any actions that need to be taken. Refer to the SoDA for reporting instructions.

### **6.2.4. Accountability**

#### **Ordering and Receipt of Investigational Product**

Procedures for ordering and receipt of BTG-002814 will be provided in the SoDA.

### **Compliance and Accountability Procedures**

Biocompatibles UK Ltd will supply BTG-002814 for use within this study only to approved investigational sites with an authorised investigational pharmacist as designated by the Investigator. The investigational pharmacist is responsible for accurate documentation of receipt, inventory, storage, preparation, and dispensing of BTG-002814.

Additional instructions on BTG-002814 accountability will be provided in the SoDA.

### **Unused Supplies**

At the end of the study, or as instructed by the Sponsor or designee, all unused BTG-002814 provided for use in this study must be returned to Biocompatibles UK Ltd/designee or destroyed according to instruction detailed within the SoDA once full accountability has been completed. Destruction must not occur at site without prior approval from the Sponsor.

## 7. STUDY PROCEDURES

### 7.1. Study Schedule

See Section 2, Schedule of Visits for the study schedule and the sequence of study procedures.

### 7.2. Schedule of Visits, Procedures, and Evaluations

#### 7.2.1. Visit 0: Screening (up to 7 days before registration)

The following assessments and procedures are required to evaluate the eligibility of patients prior to entry. Results from assessments or procedures carried out as part of routine practice may be used to assess eligibility, as long as they were carried out according to the timeframe and specification in the protocol. Patients must give written informed consent before any trial specific screening investigations may be carried out.

- Written Informed consent will be obtained, as described in section 7.3.1
- All patients who have signed the Informed Consent form will be included on the Screening and Enrolment Log. If the patient fails to fulfil the eligibility criteria, the Screening and Enrolment Log must be completed with the reason for the failure.
- Patient demographic information will be collected, as described in section 7.3.2
- Eligibility to participate in the study will be assessed, as described in section 7.3.17
- Child Pugh assessment (HCC patients only), as described in section 7.3.17
- Medical history information will be collected, as described in section 7.3.3
- Physical examination will be conducted, as described in section 7.3.4
- Vital signs will be taken, as described in section 7.3.5
- Performance status will be assessed, as described in section 7.3.6
- Medications and prior treatments will be recorded, as described in section 7.3.7
- Adverse events will be recorded and assessed as described in section 7.3.21
- Blood samples for biochemistry, haematology and coagulation, as described in section 7.3.8
- A 12-lead ECG will be taken as described in section 7.3.12
- Blood sample for serum pregnancy test for all patients of child-bearing potential, as described in section 7.3.9

#### 7.2.2. Visit 1: Baseline Visit (up to 7 days before treatment)

Following fulfilment of the inclusion and exclusion criteria and registration of the patient, the following assessments and procedures are required to be done within 7 days prior to treatment with BTG-002814:

- Liver MRI, incorporating Dynamic Contrast Enhanced MRI (DCE-MRI), as described in section 7.3.11
- CT scan of chest, abdomen & pelvis, incorporating perfusion CT of liver, as described in section 7.3.11
- Blood sample for biomarkers, as described in section 7.3.13
- Blood sample for serum tumour markers, as described in section 7.3.10
- Record any concomitant medications, as described in section 7.3.20
- Adverse events will be recorded and assessed as described in section 7.3.21

The following tests and procedures do not need to be repeated if carried out within 7 days prior to treatment with BTG-002814 as part of screening work up:

- 
- 

Physical examination will be conducted, as described in section 7.3.4

Vital signs will be taken, as described in section 7.3.5

- Performance status will be assessed, as described in section 7.3.6
- Blood samples for biochemistry, haematology and coagulation, as described in section 7.3.8
- A 12-lead ECG will be done as described in section 7.3.12
- Blood sample for serum pregnancy test for all patients of child-bearing potential, as described in section 7.3.9

### 7.2.3. Visit 2: Treatment Day

**NB: Treatment should NOT be scheduled to take place on a Friday, due to the assessments required to be performed the day after treatment (Visit 3).**

#### Pre-treatment Assessments

The following scans will be performed within a day prior to administration of BTG-002814:

- Liver MRI, incorporating DCE-MRI, as described in section 7.3.11
- CT scan of chest, abdomen & pelvis, incorporating perfusion CT of liver, as described in section 7.3.11

The following assessments and procedures will be performed on the day of treatment prior to administration of BTG-002814:

- Vital signs will be taken, as described in section 7.3.5
- Record any concomitant medications, as described in section 7.3.20
- Record any adverse events, as described in section 7.3.21
- A 12-lead ECG will be taken, as described in section 7.3.12
- Blood sample for biomarkers, as described in section 7.3.13
- Blood sample for serum tumour markers, as described in section 7.3.10
- Blood sample for vandetanib and metabolite analysis, as described in section 7.3.14

#### Post-treatment Assessments

The following assessments and procedures will be performed on the day of treatment after administration of BTG-002814:

- Vital signs will be taken, as described in section 7.3.5. Peak heart rate (HR) and peak blood pressure (BP) should be recorded in the CRF
- Record any concomitant medications, as described in section 7.3.20
- Record any adverse events, as described in section 7.3.21
- A 12-lead ECG will be taken, as described in section 7.3.12
- Blood samples for vandetanib and metabolite analysis at 2 and 4 hours after treatment, as described in section 7.3.14

### 7.2.4. Visit 3 (Day 1 after treatment)

The following assessments and procedures will be performed:

- Vital signs will be taken, as described in section 7.3.5
- Record any concomitant medications, as described in section 7.3.20
- Record any adverse events, as described in section 7.3.21

- 
- 

- Blood samples for biochemistry and haematology, as described in section 7.3.8
- 4D CT scan of liver will be performed, as described in section 7.3.11
- Blood sample for biomarkers, as described in section 7.3.13
- Blood sample for vandetanib and metabolite analysis, as described in section 7.3.14

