# 1. SCHEMA

# 2. SCHEDULE OF VISITS

Study Visit	Visit 0	Visit 1	Visit 2	Visit 3	Visit 4 	Visit 5	Visit 6
	Screening	Baseline	Treatment Day				End of Study

Assessment	Up to 7 days before registration	Up to 7 days before treatment and following registration	Pre-treatment	Posttreatment	Day 1 after treatment	Up to 3 days prior to surgical resection	Surgical resection (7 to 21 days after treatment)	28-32 days postsurgery
Informed Consent	X							
Patient Demographics	X							
Medical and Prior Treatment History	X							
Eligibility Assessment (Inclusion/Exclusion Criteria)	X							
Child Pugh Assessment (HCC patients only)	X							
Physical Examination	X	X 				X		X
Vital Signs	X	X 	X	X	X	X	X	X
WHO Performance Status	X	X 				X		X
Concomitant Medications	X	X	X	X	X	X	X	X
Assessment of Adverse Events	X	X	X	X	X	X	X	X
Biochemistry	X	X 			X	X		X
Haematology	X	X 2			X	X		X
Coagulation Tests	X	X 2				X		X
12-Lead ECG	X	X 2	X	X		X		X
Serum Pregnancy Test 	X	X 2						
Liver MRI, Incorporating DCE-MRI		X	X 			X		
CT scan chest, abdomen, liver, pelvis, incorporating perfusion CT of liver		X	X 			X		
4D CT scan liver					X			
Blood Biomarker Analysis		X	X		X	X		X
Serum Tumour Markers (AFP for HCC patients; CEA, CA19-9, CA125 for mCRC patients)		X	X			X		

Study Visit	Visit 0	Visit 1	Visit 2		Visit 3	Visit 4 	Visit 5	Visit 6
	Screening	Baseline	Treatment Day					End of Study
Assessment	Up to 7 days before registration	Up to 7 days before treatment and following registration	Pre-treatment	Posttreatment	Day 1 after treatment	Up to 3 days prior to surgical resection	Surgical resection (7 to 21 days after treatment)	28-32 days postsurgery
Vandetanib and N-desmethyl metabolite plasma sampling (0 min, 2hr ( $\pm$ 15 mins), 4hr ( $\pm$ 15 mins), 24h ( $\pm$ 1 hour), and up to hospital discharge  ) in addition to Visits 4 and 6			X	X	X	X		X
Vandetanib and N-desmethyl metabolite tissue sampling, histopathological and biomarker analysis							X	

1. For women of child-bearing potential. A negative pregnancy test must be obtained prior to treatment
2. Do not need to be repeated if screening assessments performed within 7 days prior to treatment
3. May be performed the day before treatment
4. Optional one additional plasma sample can be taken after 36 hours and up to time of hospital discharge

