#### Pre-clinical background of BTG-002814

The safety of the vandetanib-eluting bead has been evaluated in a GLP swine liver embolisation model. In this model, vandetanib-loaded RO beads (100 mg vandetanib per 1 mL bead) were delivered to healthy liver by hepatic intra-arterial administration. Up to 1 mL of vandetanib-loaded bead was administered, which equates to delivery of 100 mg vandetanib to the targeted liver lobe. The animals were maintained for either 30 or 90 days. There were no treatment-related effects evident in parameters evaluated, namely, clinical observations, body weight, ophthalmoscopy, ECG, and organ weights. Transient changes in coagulation and clinical chemistry parameters were observed, likely to be related to the hepatic embolisation procedure.

There were expected microscopic findings associated with hepatic embolisation following intrahepatic administration of vandetanib-loaded bead. The study indicated that intrahepatic administration of up to 1 mL vandetanib-loaded RO bead containing 100 mg of vandetanib was well tolerated, did not produce any obvious systemic toxicity and resulted in nothing more than expected microscopic findings associated with hepatic embolisation and subsequent healing.

In an efficacy study conducted in a rabbit model, VX-2 carcinoma tumours were implanted in the liver, followed by hepatic intra-arterial administration of DC Bead loaded with vandetanib up to 135 mg/mL (DCV). DCV showed equivalent anti-tumoural activity to doxorubicin-loaded bead and superior anti-tumoural activity compared to bland (unloaded) bead. Single hepatic administration of DCV showed equivalent anti-tumoural efficacy to repeat dose of oral vandetanib, at the doses administered (~5.4 mg per animal with DCV vs 1470 mg oral vandetanib, respectively). Compared to oral dosing, it is notable that DCV showed a lower plasma concentration and a higher tumour concentration of vandetanib relative to the total dose administered.

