### 7.2.5. Visit 4 (Up to and including 3 days prior to surgical resection)

The following assessments and procedures will be performed:

**NB: if surgery is delayed by > 7 days, all visit 4 assessments should be repeated up to and including 3 days before the rescheduled surgery.**

- Physical examination will be conducted, as described in section 7.3.4
- Vital signs will be taken, as described in section 7.3.5
- Performance status will be assessed, as described in section 7.3.6
- Record any concomitant medications, as described in section 7.3.20
- Record any adverse events, as described in section 7.3.21
- Blood samples for biochemistry, haematology and coagulation, as described in section 7.3.8
- A 12-lead ECG will be taken, as described in section 7.3.12
- Liver MRI, incorporating DCE-MRI, as described in section 7.3.11
- CT scan of chest, abdomen & pelvis, incorporating perfusion CT of liver, as described in section 7.3.11.
- Blood sample for biomarkers, as described in section 7.3.13
- Blood sample for serum tumour markers, as described in section 7.3.10
- Blood sample for vandetanib and metabolite analysis, as described in section 7.3.14

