### **Coagulation Parameters**

Blood samples for coagulation parameters will be taken.

- Prothrombin Time (PT)
- Partial Thromboplastin Time (PTT)
- International Normalised Ratio (INR)

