6.2. Tumour size/measurement

- The longest diameter of each lesion (mm) is measured at baseline and again on the day before surgical resection.
- The sum of the diameters can be taken for each patient, using the same lesions.
- Produce a waterfall plot showing the change in the sum from baseline to pre-surgery.
- Change in tumour size can also be compared using a paired t-test or Mann-Whitney test, depending on whether Normally distributed or not.
- Waterfall plot obtained for all patients, then separately for HCC and mCRC.

7. Concomitant Medications

Patient ID	Drug name/type	Time (days) from day of BTG treatment to start of non-trial drug
1	A	
1	B	
1	C	
2	D	
2	E	
2	F	

8. Follow up and deaths

	All patients	HCC	mCRC
	n (%)	n (%)	n (%)
No. patients who died			
Cause of death			
No. patients who dropped out/withdrew from the trial			
Reasons for withdrawal			
Lost to follow up			

9. Other Safety Parameters

Other safety parameters such as ECG, vital signs and physical examinations will be summarised

For laboratory parameters, observed values, changes from baseline, shifts in CTC grade and normal values/above and below normal values will be summarised with descriptive statistics. A listing of individual laboratory data will be provided with values outside normal ranges flagged.

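### Coagulation is not sampled on Day 1, so a change that resolves before Visit 4 (about Day 4 to Day 20) can go unrecorded

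*Protocol*

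**What the plan says.** **Day 1 (Visit 3).** Protocol 7.2.4 lists "Blood samples for biochemistry and haematology, as described in section 7.3.8". The Schedule of Visits matches: the row "Coagulation Tests" is marked at Visits 0, 1, 4 and 6 and is blank at Visits 2 and 3, whereas biochemistry and haematology are also marked at Visit 3.

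**Treatment day.** The post-treatment list in Protocol 7.2.3 contains no coagulation sample.

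**The panel.** Protocol 7.3.8 treats PT, PTT and INR as a panel of their own ("Blood samples for coagulation parameters will be taken"), so the Day 1 biochemistry and haematology samples do not cover them.

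**Before surgery (Visit 4).** Protocol 7.2.5 lists "Blood samples for biochemistry, haematology and coagulation, as described in section 7.3.8".

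**Preclinical finding.** Protocol 3.3 reports from the swine embolisation study: "Transient changes in coagulation and clinical chemistry parameters were observed, likely to be related to the hepatic embolisation procedure".

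**Analysis.** SAP section 9 states: "For laboratory parameters, observed values, changes from baseline, shifts in CTC grade and normal values/above and below normal values will be summarised". Protocol 9.5.2 plans the same. SAP 4.1.1 and 4.1.2 each include a version of the adverse event table limited to the day after treatment.

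**The concern.** The sponsor's animal study names two groups of laboratory tests that moved transiently after embolisation. One of them, clinical chemistry, has a sample on the day after treatment. The other, coagulation, does not, and the documents give no reason for the difference.

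This is the first study of the product in humans, and treatment-related adverse events are a co-primary endpoint. Under Protocol 7.3.8 a laboratory change becomes an adverse event only when the investigator judges it clinically significant, and that requires a measurement. A coagulation change without symptoms on Day 1 therefore has no systematic way into the Day 1 adverse event table. The same holds for the interim review of the first three patients, which under Protocol 9.6 looks at baseline data, treatment details and adverse events. At stake is how far an absence of early coagulation findings can be read as evidence that there were none.

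**Working it through.** The study is descriptive and has no power calculation, and the plan states no figure for the day of the first post-treatment coagulation test. The check is day arithmetic on the plan's own windows.

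**Inputs**
- Treatment is Day 0 (SAP 4.1.2).
- Surgery is on Day 7 to Day 21: "All patients will receive one treatment of BTG-002814 between 7 and 21 days prior to surgery" (Protocol 6.1.4).
- Visit 4 is "Up to and including 3 days prior to surgical resection" (Protocol 7.2.5). The SAP's list of plasma time points (4.2.1) puts the pre-surgery sample 3 days to 1 day before surgery. I apply that 1-day bound to Visit 4 as a whole, which is an assumption.

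**Step 1: day of the first scheduled post-treatment coagulation value**

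Visit 4 day = surgery day − offset.
- Earliest: 7 − 3 = Day 4
- Latest: 21 − 1 = Day 20

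Other readings of the window:
- Visit 4 always the day before surgery: 7 − 1 = Day 6 to 21 − 1 = Day 20.
- Day of surgery also allowed: 7 − 3 = Day 4 to 21 − 0 = Day 21.

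**Step 2: gap relative to the Day 1 draw**

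4 − 1 = 3 days to 20 − 1 = 19 days. In the first 3 days after treatment there are 0 scheduled coagulation tests, against 1 for biochemistry and 1 for haematology.

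**Step 3: how long a change must last to meet a scheduled sample**

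There are 15 surgery days (7 to 21) and 3 offsets (1, 2, 3), so 15 × 3 = 45 combinations. A change that begins soon after treatment and is still present on Day L is sampled only if Visit 4 falls on or before Day L.

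| Change lasts to | Combinations with a scheduled sample by then | Share |
|---|---|---|
| Day 3 | 0 of 45 | 0% |
| Day 4 | 1 of 45 | 2% |
| Day 7 | 9 of 45 | 20% |
| Day 10 | 18 of 45 | 40% |
| Day 14 | 30 of 45 | 67% |
| Day 20 | 45 of 45 | 100% |

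The shares treat all combinations as equally likely and are illustrative only. The zero for Day 3 does not depend on that weighting.

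**Step 4: with coagulation added at Visit 3**

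The first post-treatment value falls on Day 1 for every patient. Day 2 and Day 3 would still have no scheduled sample, as is already the case for biochemistry and haematology.

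**The case against.** The strongest reply is that nothing in the plan is in error. Text and schedule agree, and the revision history shows that the timing of the post-treatment laboratory tests was considered, since biochemistry and haematology were moved from Visit 2 to Visit 3. That entry does not mention coagulation. It is fair to treat the omission as a design choice.

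Four further points limit what can be claimed:

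- **Duration is unknown.** Protocol 3.3 gives no onset, size or duration for the swine changes, and the animals were kept for 30 or 90 days. A reader might infer that a transient effect will be missed, or that the coagulation summary would look flat even if every patient had a change. The documents do not support that. Only a change that has gone before Visit 4 is certain to escape the scheduled data. For the same reason, one Day 1 sample is not guaranteed to catch it.
- **Surgery.** A reader might infer that patients reach resection without a coagulation check. They do not: Visit 4 includes one, and Visit 4 is repeated if surgery slips by more than 7 days.
- **Endpoint.** Laboratory shifts are not the co-primary endpoint; treatment-related adverse events are. Clinical consequences such as bleeding would be recorded at the treatment and Day 1 visits, and patients stay overnight.
- **SAP section 9** does not claim that all laboratory panels were sampled equally, and its individual data listing would show that Day 1 coagulation values are absent.

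The protocol also attributes the swine changes to the embolisation procedure rather than to the drug. That does not put them out of scope: Protocol 8.1.4 has relatedness to vandetanib and to the beads/TACE procedure assessed separately, and the SAP tabulates TACE-related events.

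Two routes could supply early values: unscheduled bloods, which feed the SAP's adverse event tables, and the extra INR monitoring recommended for users of vitamin K antagonists (Protocol 6.1.5). Neither is systematic. They narrow the gap without closing it.

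**Conclusion.** The point holds as a gap in ascertainment. No coagulation test is scheduled between treatment and Visit 4, which falls on about Day 4 to Day 20, while the other test group flagged in swine is sampled on Day 1. A coagulation change that resolves before Visit 4 would not appear in the scheduled values, in the summaries of change from baseline and CTC grade shift, or, if clinically silent, in the Day 1 adverse event table. The same limit applies to the adverse events seen at the interim review.

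The size is a delay of 3 to 19 days in the first post-treatment value. This rests on surgery taking place on Day 7 to Day 21 and Visit 4 being 1 to 3 days before it. Whether any patient has such a change cannot be judged from the documents. The pre-operative value is not affected, and no contradiction between passages needs reconciling. This is a low-cost improvement to safety data in a first-in-human study.

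**What to change.** Add PT, PTT and INR to the Visit 3 draw in Protocol 7.2.4, and mark Visit 3 in the coagulation row of the Schedule of Visits. In SAP section 9, report the Day 1 coagulation change with the other Day 1 laboratory changes.

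For patients already treated, use any Day 1 coagulation result held by the local laboratory, and state beside the coagulation tables that no Day 1 value was scheduled.

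The cost is one extra tube at a draw that already takes biochemistry, haematology, biomarker and vandetanib samples, one local laboratory test and a minor amendment. The change concerns data collection only and sets no dose or treatment rule.
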